8.2.2. Analysis of Secondary Endpoints

The following analyses will address the secondary CCI [REDACTED] immunogenicity objectives.

The primary endpoints (percentage of subjects with hSBA titer \geq LLOQ to each of the 4 primary strains at 1 month postdose 3) will be analyzed in the 2 age strata combined. 95% confidence intervals (CIs) will be presented along with the response rate. This will be done for the evaluable and the mITT populations.

The proportions of subjects achieving hSBA titers \geq LLOQ for each of the 4 primary strains at 1 month after the second vaccination and 6 months after the third vaccination will be analyzed in the 2 age strata separately and combined, in the evaluable and the mITT population. Analysis will be the same for the primary endpoints.

The proportions of subjects achieving hSBA titers of \geq 1:4, \geq 1:8, \geq 1:16, \geq 1:32, \geq 1:64, and \geq 1:128 for each of the 4 primary test strains at baseline, 1 month after the second vaccination, and 1 and 6 months after the third vaccination will be analyzed in the 2 age strata separately and combined, in the evaluable and the mITT population. Analysis will be the same for the primary endpoints.

The hSBA GMTs for each of the 4 primary test strains at baseline, 1 month after the second vaccination, and 1 and 6 months after the third vaccination will be analyzed in the 2 age strata separately and combined, in the evaluable and the mITT population. GMTs and 95% CI will be presented.

The empirical reverse cumulative distribution curves (RCDCs) will be presented graphically for each of the 4 primary strains and at each sampling time point, for the evaluable population.

8.2.3. Analysis of Exploratory Endpoints

CCI

8.2.4. Additional Analyses of Immunogenicity

8.2.4.1. Assessing Missing hSBA with Other Variables

All of the subjects, for the combined age strata, will be dichotomized to 2 categories – with missing hSBA or non-missing hSBA. If a subject has missing data at any blood sampling visit for any strain, the subject will be categorized as ‘Missing (1)’; if the subjects have hSBA data for all blood sampling visit for all strains, the subjects will be categorized as ‘Non-missing (0)’. Then the summary statistics will be provided for the following variables by the missing indicator:

Age (mean, std), Race, Gender, Center, Vaccine Group, GMT on each strain for each group at each visit.

Additional summaries may be provided based on each primary strain, where the Missing (1) will be assigned to subject with missing data at any blood sampling visit for that strain and the non-Missing (0) will be assigned to subject with all 3 time points for that strain. The same variables will be summarized for each indicator.

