## **9.2. Immunogenicity Analysis**

This is not a hypothesis-testing study; thus, an estimation approach will be used to assess the primary, secondary, and exploratory objectives.

As assay data are expected to be missing completely at random (MCAR) (Scott & Hsu, 2011), the primary analysis for the primary objectives will be based upon the observed, determinate observations. If all subjects have hSBA tested for all of the 4 primary MnB test strains, descriptive summaries will be provided to describe the hSBA data missing reason and the relationship between the missing data indicator and other design variables or covariates (age, race, gender, center, etc) and the observed hSBA data. Additionally, a sensitivity analysis using mixed effects model with repeated measurement (MMRM) will be applied to the primary endpoints. The MMRM uses the maximum likelihood estimation, and it is under the assumption that the missing is at random (MAR). If 50% of the subjects or less have 2 strains tested and the remaining have the other 2 strains tested, no sensitivity analyses will be planned because the missing assumption is MCAR.

For the calculation of GMTs, hSBA results below LLOQ will be set as  $\frac{1}{2}$  of LLOQ as primary analysis.

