2.1.2. Assessments

Subjects will receive investigational products at Visit 1, 3, and 5. All of the subjects will have a blood draw for immunogenicity assessment at Visits 1, 4, 6 and 7, which is at baseline, 1 month post-vaccination 2, 1 month post-vaccination 3 and 6 months post-vaccination 3 respectively.

Reactogenicity data, including local reactions, systemic events (including fever), and use of antipyretics will be collected via an electronic diary (e-diary) completed for each subject for 7 days following each vaccination.

Adverse events (AE) will be collected from the signing of the informed consent document (ICD) to Visit 6 (1 month post-vaccination 3 blood draw). Serious Adverse Events (SAE), medically attended (non-serious) adverse events, and newly diagnosed chronic medical conditions will be collected throughout the study. In addition, AE within 30 minutes after investigational product administration will be documented.

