7. HANDLING OF MISSING VALUES

7.1. Immunogenicity Data

For the hSBA assay results, the following values will be set to missing: QNS (insufficient sera), indeterminate results, and Not Done. Subjects without a blood draw (eg, dropouts) will also have missing immunogenicity data.

The primary immunogenicity analyses will use only valid and determinate assay results with no imputation of missing values, which uses the assumption that data are missing completely at random (MCAR).¹ The approach to missing assay data depends on serology testing strategy, to be determined:

- If volume permits, subjects will have serum tested for all 4 primary strains by hSBA. In this case, descriptive summaries will explore the relationship between the missingness indicator and design variables or covariates (age, race, gender, site etc.). A sensitivity analysis using a mixed effects model with repeated measurement (MMRM) will be applied to the primary immunogenicity endpoints.

- If only 50% of subjects are tested for 2 of the 4 primary strains, and the other 50% of subjects tested for the other 2 primary strains, there will be no sensitivity analysis. Data will be assumed to be MCAR.

For the calculation of GMTs, hSBA values below LLOQ will be assigned a value of half the LLOQ. The LLOQ for CCI (A22) is 1:16, and for the other 3 primary test strains is 1:8.

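### SAP 8.2.4.1 misdefines its missing-hSBA indicator: three time points are asked for where four are planned, and strains a subject was never tested on count as missing if only some subjects are retested

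*SAP*

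**What the plan says.** SAP 8.2.4.1 plans a descriptive comparison of subjects with and without missing hSBA. It states: "All of the subjects, for the combined age strata, will be dichotomized to 2 categories". The main rule is broad: "If a subject has missing data at any blood sampling visit for any strain, the subject will be categorized as" Missing (1). Non-missing (0) requires hSBA data for every strain at every sampling visit. Age, race, gender, center, vaccine group and GMTs are then summarised by this indicator.

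An optional version works strain by strain. Any missed sampling visit for the strain again gives Missing, but "the non-Missing (0) will be assigned to subject with all 3 time points for that strain".

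Four other places bear on this:
- **SAP 2.1.2** on sampling: "All of the subjects will have a blood draw for immunogenicity assessment at Visits 1, 4, 6 and 7".
- **SAP 7.1** on what counts as missing: "the following values will be set to missing: QNS (insufficient sera), indeterminate results, and Not Done".
- **SAP 2.1.3** assigns each subject two of the four strains and adds the other two where enough serum remains.
- **SAP 7.1 and Protocol 9.2** set the condition for missingness summaries. The SAP's first branch reads "If volume permits, subjects will have serum tested for all 4 primary strains by hSBA", and the summaries and an MMRM follow. Its second branch, "If only 50% of subjects are tested for 2 of the 4 primary strains" and the other half for the other two, has no sensitivity analysis. The protocol's condition is stricter: "If all subjects have hSBA tested for all of the 4 primary MnB test strains, descriptive summaries will be provided".

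**The concern.** The per-strain wording conflicts with the sampling schedule and with itself, so two programmers could build different tables from it.

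The main rule makes no exception for strains a subject was never selected for. With not-done results set to missing, a child who has every assigned result but no retest is classed with children who dropped out or gave too little serum.

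The primary analysis assumes that hSBA data are missing completely at random, and this is the only planned table that directly contrasts subjects with and without missing hSBA. If its Missing column partly records who was retested, it says little about that assumption.

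**Working it through.** **1. How many time points.** Inputs: 400 subjects (SAP 2.1.1); two strains each under the split, or four if all are tested (SAP 2.1.3).
- Four time points: 400 × 2 × 4 = 3,200 and 400 × 4 × 4 = 6,400. Both reproduce the SAP 2.1.3 totals.
- Three time points: 400 × 2 × 3 = 2,400 and 400 × 4 × 3 = 4,800. Neither does.

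The plan is therefore built on four draws. The model in SAP 8.2.4.2 also treats baseline as an outcome, which does not suit a post-vaccination-only count of three.

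**2. Overlap in the per-strain rule.** Each of four visits is present or absent, giving 2^4 = 16 patterns. The first clause makes 15 of them Missing (all but the complete one). If three means three fixed visits, such as the post-vaccination draws, 2 patterns are non-Missing: those three present, with the fourth present or absent. The second of these is also Missing. One pattern thus fits both categories: a subject lacking only the visit outside the three.

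**3. What the main rule demands.** Non-missing needs 6,400 / 400 = 16 results per subject. The split plans 3,200 / 400 = 8. A subject with all assigned results and no retest has 8 of 16 and is Missing.

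**4. Partial retesting.** The documents do not say how many subjects will be retested, so n is an assumed range. Of 400 subjects, 400 − n are Missing because they were not retested. If a share k of these also lost an assigned result, (400 − n)(1 − k) have every assigned result; k is assumed to be 0% to 10%.

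| n retested (assumed) | Missing because not retested (400 − n) | Share of 400 | Of these, all assigned results present (k = 0% to 10%) |
|---|---|---|---|
| 100 | 300 | 75% | 300 to 270 |
| 200 | 200 | 50% | 200 to 180 |
| 300 | 100 | 25% | 100 to 90 |
| 360 | 40 | 10% | 40 to 36 |

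Retested subjects with real loss add to the Missing column on top of these.

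**5. Link to vaccine group (conditional).** Protocol 7.1.3 names bivalent rLP2086 recipients when it describes retesting; SAP 2.1.3 sets no group limit. If only that group were retested, the maximum would be 3,200 + 300 × 2 × 4 = 5,600 results, and all 100 controls would be Missing. With all 300 retested and nothing lost, Missing would be 0 of 300 against 100 of 100, or 100 / 400 = 25% overall.

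**The case against.** Several points on the other side have force.

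- **The table is conditional.** SAP 7.1 and Protocol 9.2 plan missingness summaries only under four-strain testing, where the main rule fits. A reader might infer that the planned 50/50 split would make every subject Missing. The documents do not support that, unless 8.2.4.1 is run without the condition, which it does not repeat. Partial retesting remains uncovered. Protocol 7.1.3 aims at four-strain data for as many subjects as serum allows, and neither SAP 7.1 branch describes a mixture. The SAP's first branch also omits the protocol's requirement that all subjects be tested.
- **Not retested is not the same as loss-free.** A reader might take the 300, 200, 100 or 40 as subjects with no data lost. That goes too far. Some will have withdrawn or lost an assigned result. Serum volume is the stated limit on retesting, and insufficient serum is real missingness under SAP 7.1. It could follow age, because Protocol 7.1 targets 5 mL below 4 years and about 10 mL from 4 years.
- **The slip over three time points is editorial.** The per-strain table is optional and the sentence's first clause shows the intent. Reading it as any three of four would make 4 patterns overlap, but the words hardly bear that.
- **Retesting of controls is ambiguous, not contradictory.** The wording in Protocol 7.1.3 is permissive, and the 6,400 in SAP 2.1.3 is itself conditional.
- **Other views exist.** Protocol 9.2 also plans summaries of the reasons for missing data, under the same condition. Denominators and the disposition and blood-draw tables (SAP 8.2.6.1) give an indirect picture. None of these repairs the indicator.

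**Conclusion.** The concern holds at minor severity. The per-strain rule is wrong as written: it names three time points where the plan has four, and at least one visit pattern falls in both categories. This needs no assumption beyond reading three as three fixed visits.

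The any-strain problem is conditional. It arises only if the table is run when some but not all subjects are retested, or outside the SAP 7.1 and Protocol 9.2 condition. Then 400 − n subjects are Missing because they were not retested: 300, 200, 100 or 40 for the assumed n of 100, 200, 300 or 360. The link with vaccine group rests further on one reading of Protocol 7.1.3.

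A reader might infer that the primary results are affected. They are not: this is a descriptive diagnostic and no primary estimate changes.

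**What to change.** In SAP 8.2.4.1:
1. Replace the three time points with all four visits (1, 4, 6 and 7).
2. Define the indicator per strain, among subjects assigned to that strain or selected for retesting on it. Missing means no valid, determinate result at one or more of the four visits, counting insufficient serum, indeterminate results and missed draws. Non-missing means valid, determinate results at all four.
3. Show subjects not selected for testing on the strain as a separate category, kept apart from insufficient serum.
4. Cross-refer to the SAP 7.1 condition and state what applies when only some subjects are tested on all four strains.
5. Clarify across Protocol 7.1.3 and SAP 2.1.3 whether control samples may be retested.

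The cost is wording in one SAP section, a cross-reference, one clarifying clause and minor table programming. No extra assays or blood are needed.

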8.2.4.2. Assessing Factors of Age, Race, Center, and Gender on GMT

A mixed-effect model with repeated measurement (MMRM)⁶ will be utilized to assess the effect of age, race, center and gender, in which both baseline and the postvaccination titers (in logarithmic scale) are modeled as dependent variables for each primary strain. This model is using maximum likelihood estimation, therefore, it also serves as a sensitivity analyses on missing data for the GMT. To account for the intrasubject correlation among the repeated measures, an unconstrained covariance matrix will be used. In case the model does not converge, further covariance structures will be explored (eg, autoregressive, compound symmetry).

Log (hSBA) = Group + center + race + gender + age at randomization +visit+ Group* visit.

The intercept will be set as a random effect.

Site may be used as centers. However, several sites maybe pooled to one center depending on geographic location (if size <5 within the site). In the case of non-convergence, country may be used as center.

In addition to Type III analysis output, least squares GMT at each visit for each group will be summarized for each strain.

This analysis will only be applied to subjects in the combined age strata in the mITT population, using $\frac{1}{2}$ LLOQ to impute the hSBA values below LLOQ.

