8.1.1. Analyses for Continuous Data

For each of the 4 primary strains, hSBA titers will be logarithmically transformed for analysis and Geometric mean titers (GMTs) will be computed with 95% confidence intervals (CI) for each group. The 2-sided, 95% CI for the GMTs will be constructed by back transformation of the confidence intervals for the mean of the logarithmically transformed titers computed using the Student t distribution.

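### The GMT mixed model in SAP 8.2.4.2 gives vaccine and control one covariance matrix, so its post-vaccination standard errors fit neither group if control titers vary less

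*SAP*

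**What the plan says.** SAP 8.2.4.2 fits a mixed model for each primary strain in the mITT population, age strata combined, in which "both baseline and the postvaccination titers (in logarithmic scale) are modeled as dependent variables for each primary strain". The mean model is "Log (hSBA) = Group + center + race + gender + age at randomization +visit+ Group* visit", with a random intercept. On covariance the section says "To account for the intrasubject correlation among the repeated measures, an unconstrained covariance matrix will be used", and on non-convergence: "In case the model does not converge, further covariance structures will be explored (eg, autoregressive, compound symmetry").

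The promised output is Type III tests, and "least squares GMT at each visit for each group will be summarized for each strain". No confidence interval is named for these least squares GMTs. The section gives the model a second role: because it uses maximum likelihood, "it also serves as a sensitivity analyses on missing data for the GMT".

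The main GMT analysis is built differently. In SAP 8.1.1, "Geometric mean titers (GMTs) will be computed with 95% confidence intervals (CI) for each group", using the Student t distribution within each group.

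**The concern.** Group enters only the mean. An unconstrained matrix lets variances and correlations differ between visits, but not between groups, and the random intercept is a further shared variance. The natural reading is one matrix common to vaccine and control, although the text does not say so outright.

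Three features of the design suggest that post-vaccination variances will differ:

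- Control receives HAV vaccine, saline and HAV vaccine, with no MnB antigen (SAP 2.1).
- Prior serogroup B vaccination is an exclusion criterion (Protocol 4.2).
- Every value below LLOQ is replaced by one constant, half the LLOQ (SAP 7.1 and 8.2.4.2). A group with many such values has little spread.

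A pooled variance is then too small for vaccine and too large for control. This reaches the Type III tests directly, and any intervals put on the least squares GMTs. It also blurs the sensitivity role: beside SAP 8.1.1 the model changes the variance assumption as well as the missing-data assumption, so a change in precision cannot be put down to missing data.

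**Working it through.** **Counts in the plan.** SAP 2.1.3 gives about 3,200 hSBA results: 200 subjects x 2 strains x 2 halves x 4 visits = 3,200. Testing all strains in everyone gives 400 x 4 x 4 = 6,400. Both match the SAP. Protocol 7.1.2 keeps 3:1 within each half, so each strain has about 150 vaccine and 50 control subjects (300 and 100 if all are tested).

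**Inputs not in the documents.** Neither document gives a titer SD or a control seropositivity rate. Everything below is therefore a function of SDv (vaccine) and SDc (control), over an assumed range.

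**Formulas** (complete data, Group-by-visit means, one common matrix, at a given visit):

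- Pooled variance = 0.75 SDv² + 0.25 SDc²
- Vaccine width factor = pooled SD / SDv; control width factor = pooled SD / SDc
- Approximate vaccine coverage = 2Φ(1.96 x vaccine factor) − 1
- Difference between groups, pooled SE / correct SE = √[(3SDv² + SDc²) / (SDv² + 3SDc²)]

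| SDv/SDc | Vaccine factor | Vaccine coverage | Control factor |
|---|---|---|---|
| 1.5 | 0.93 | 93.1% | 1.39 |
| 2 | 0.90 | 92.3% | 1.80 |
| 3 | 0.88 | 91.6% | 2.65 |
| 5 | 0.87 | 91.2% | 4.36 |
| 10 | 0.87 | 91.1% | 8.67 |

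The vaccine factor cannot fall below √0.75 = 0.866: at most 13% too narrow, with coverage of at least 91.0%. The control factor has no such cap. It reaches 2 at a ratio of 2.24 and 3 at 3.42.

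**Link to seropositivity.** Assume LLOQ 8 with lower values set to 4. Titers at or above LLOQ are centred at log2 5 (SD 1.5) in vaccine and log2 4 (SD 1.2) in control. With 50% to 95% of the vaccine group at or above LLOQ, SDv is 1.49 to 1.84 log2.

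| Controls at or above LLOQ | SDc (log2) | Control factor |
|---|---|---|
| 1% | 0.24 | 5.3 to 6.6 |
| 2% | 0.34 | 3.8 to 4.7 |
| 5% | 0.54 | 2.5 to 3.0 |
| 10% | 0.74 | 1.8 to 2.2 |
| 20% | 1.00 | 1.4 to 1.7 |
| 40% | 1.27 | 1.1 to 1.4 |

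This mapping depends on the assumed shape of the titer distribution; the table of SD ratios does not.

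**Example.** SDv 1.7, SDc 0.3: pooled SD = √(0.75 x 2.89 + 0.25 x 0.09) = √2.19 = 1.48. With 150 and 50 subjects, the upper 95% limit as a multiple of the GMT is 1.178 pooled against 1.208 own for vaccine, and 1.329 against 1.059 for control.

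**Group difference.** In the example the ratio is √(8.76/3.16) = 1.66. For SDv 1.5 to 1.9 it runs from about 1.2 at SDc 1.0 to 1.7 at SDc 0.1, and it cannot exceed √3 = 1.73. At 40% seropositivity it is smaller: with SDv 1.49 and SDc 1.27 it is √(8.27/7.06) = 1.08.

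**Simulation check** (4,000 trials, 150 against 50, four visits, no covariates): post-vaccination coverage was 91% to 94% for vaccine and 98% to 100% for control. At baseline the groups share one distribution and the factor was about 1.0.

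**The case against.** The strongest reply is that little of what the SAP will report depends on this. Section 8.2.4.2 is an additional analysis whose first purpose is to assess covariates. It promises no interval, no bias in the least squares GMTs has been shown, and the trial has no hypotheses or decision rules (SAP 4.1 and 4.2). The primary proportions use exact intervals and the main GMT intervals use each group's own SD. All of this stands and limits the reach of the point. It does not cover the Type III tests, which are promised.

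A reader might infer that control titers hardly vary and that control intervals are several times too wide. The documents do not support that as a fact. A factor of 3 needs an SD ratio of about 3.4, which under the assumptions above means roughly 5% or fewer controls at or above LLOQ.

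A reader might also infer that the fallback structures would push vaccine coverage far lower, to about 83% at Visit 6. That needs non-convergence, compound symmetry, equal variance over visits and a set of assumed visit variances (0.08, 1.2, 1.39 and 0.9). The SAP lists its fallbacks only as examples and does not say they are the equal-variance versions. What stands is that an equal-variance version would bring baseline into the problem and remove the 13% cap.

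Two further objections bear on size. Protocol 7.1.3 allows the extra strains to be tested in bivalent rLP2086 recipients. If only those are added, a strain has about 300 against 50, and vaccine narrowing is at most 1 − √(6/7) = 7%, with coverage of at least 93%. The control and difference factors then grow: the difference ratio in the example becomes √[(6 x 2.89 + 0.09)/(2.89 + 6 x 0.09)] = 2.25. Second, SAP 7.1 plans no missing-data sensitivity analysis under split testing, although 8.2.4.2 is not made conditional on that.

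Adjustment for center, race, gender and age would also make the model differ from SAP 8.1.1. That is true, but it is no reason to add a variance misspecification.

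Finally, a separate control matrix may be singular. With 5% of 50 controls at or above LLOQ, the chance of none at a given strain and visit is 0.95^50 = 7.7%, or about 1.2 expected among 16 strain-visit cells. This stands, and the fix allows for it.

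**Conclusion.** The point holds for this supportive model. As written, it has no group-specific covariance, and the direction of the error follows whenever post-vaccination variance is larger in vaccine than in control.

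The vaccine effect is modest and bounded under 3:1 allocation with the unconstrained matrix. The control effect ranges from slight to several-fold, depending on a seropositivity rate that the documents do not give. The 1.2 to 1.7 inflation for the group difference rests on assumed control SDs of 1.0 down to 0.1 log2, and would be nearer 1.1 at 40% seropositivity. Baseline is not affected unless a fallback with equal variance over visits is used.

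Missing data and covariate adjustment were not modelled. They would change the exact factors. No conclusion about the primary endpoints or the SAP 8.1.1 GMT intervals follows from this.

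**What to change.** In SAP 8.2.4.2:

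1. State that the covariance matrix is estimated separately for each vaccine group, with robust (sandwich) standard errors.
2. State that if the control matrix cannot be estimated because nearly all control values equal half the LLOQ, the common unstructured matrix is kept with robust standard errors.
3. Replace the listed fallbacks with heterogeneous-variance versions, such as heterogeneous Toeplitz or heterogeneous compound symmetry.
4. State whether 95% confidence intervals accompany the least squares GMTs.

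The cost is a few sentences and a program option. A second four-visit matrix adds 4 x 5 / 2 = 10 covariance parameters, and non-convergence becomes somewhat more likely in control, which item 2 is there to handle. If the two variances prove similar, little is lost.
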